## **7.0 Data and Specimen Banking\***

N/A- This study does not involve data and specimen banking.

## **8.0 Sharing of Results with Subjects\***

Results of pre-/post-/follow-up survey scores/results will not be shared with individual study participants.

As described earlier, de-identified study data will be shared with CRCHD/its contractor for aggregation and evaluation.

At the commencement of the study, we plan to develop a community report to share with relevant stakeholders (e.g., DCC Community Advisory Board, cancer center researchers and clinicians, clinical trials staff, primary care providers, cancer control professionals, cancer center researchers) to learn about the study; all data in this report will be de-identified and aggregated. We will also seek opportunities to disseminate the results through academic channels, such as conferences and publications.

## **9.0 Study Timelines\***

**9.1** Participants will conclude their participation within 7.5 months from enrollment. This timeline allows for a multi-week window for obtaining the follow-up clinical trials/research study enrollment records.

We anticipate enrolling all study participants within four years of study activation as study team's grant has been extended.

Pregnant women: Any inclusion of pregnant women will be strictly incidental and will not present any added risk should they choose to participate. We will not be asking any questions pertaining to pregnancy, and we will not specifically be targeting pregnant women. Regardless of whether a person is pregnant, receiving education about clinical trials and research does not pose a risk and has the potential to be beneficial.

Prisoners: We will not be initiating any research in institutionalized

PROTOCOL TITLE: Education about Health and Cancer Study  
settings nor will we explicitly target prisoners. No questions, including screening questions, will be specifically asked about a person's incarceration status. Any inclusion of prisoners will be strictly incidental and will not present any added risk should they choose to participate.

## **11.0 Vulnerable Populations\***

**11.1** It is likely that some participants may be elderly. It is also possible that some participants will be from an economically disadvantaged background. We feel that the payment amounts we plan to provide are appropriate given the participants' time involved and are not excessive or coercive.

As stated in Section 10, our study is not targeting any of the following vulnerable populations: pregnant women, neonates/non-viable neonates, prisoners, people who have not attained legal age to consent, or cognitively-impaired adults.

## **12.0 Local Number of Subjects**

Our target sample size for completing the study is

- Experimental Arm 1: up to 50
- Experimental Arm 2: 200-250

Because of the nature of the study being primarily online, we anticipate additional people consenting into the study and not being eligible and/or not completing the study. As such, we anticipate consenting up to 900 people to have about 1/3 complete all study procedures.

## **13.0 Recruitment Methods**

13.1-13.4

### Experimental Arm 1 (Aim 1a):

To recruit participants for the evaluation/data collection, we will rely on people who are registered for an existing class at the Dartmouth Cancer Center ('Clinical Trials: Another Approach to Cancer Treatment').

See recruitment messaging document attached.

Using DHH electronic medical reporting system Epic a Best Practice Alert (BPA) for cancer providers at point of care prompts to ask patients if a connection to education survey about clinical trials can be sent to them. Patient is sent information to access survey, or, to be connected with clinical coordinator/nurse who can talk them through accessing the survey link.

### Experimental Arm 2 (Aim 1b):

We will purchase advertisements on social media (e.g., Facebook), listserves, or via flyers, which will be targeted to adults in VT/NH RUCC 7-9 counties. We will rely of Facebook's algorithms to direct our recruitment messages to individuals in the appropriate age range and geographies. Advertisements will use verbiage such

PROTOCOL TITLE: Education about Health and Cancer Study  
as:

“Researchers at the Dartmouth-Hitchcock Norris Cotton Cancer Center are looking for adults to watch a video, read some information, and answer surveys. Participation is voluntary and confidential. You will be compensated for your time. Click the “Learn more” button to learn more and to participate in this RESEARCH survey.”

We may also post the same recruitment message in unpaid social media posts and may also share our recruitment verbiage with partner organizations (e.g., Vermonters Taking Action Against Cancer, UVM, New Hampshire Department of Health and Human Services) and through other online opportunities (e.g., Front Porch Forum, e-newsletters and listservs, online community forums/groups, etc) to post our messaging in settings where their followers/members may view it (e.g., their website, social media, newsletters). See recruitment messaging document attached with sample messaging.

13.5 Participants in Experimental Arm 1 will receive a \$5 gift card/e-gift code for completing the pre-test and will receive an additional \$10 gift card/e-gift code after completing the survey and completing the post-test. Participants of Experimental Arm 2 will receive \$10 in gift cards/e-gift codes (e.g. to Amazon.com) for completing the surveys and interventions. E-gift cards that have not been claimed six months after being emailed may be deactivated.

## **14.0 Withdrawal of Subjects\***

**14.1** Study subjects will be withdrawn from the study if they do not complete the pre-test, educational intervention, and post-test—which are the minimum data we need in order to evaluate a portion of our intervention.

### **14.2**

#### Experimental Arm 1 (Aim 1a):

A person can discontinue participation at any time by indicating for any reason that they no longer wish to participate. Individuals who do not complete the in-person pre-test, education, post-survey, and contact/identifying information will not have their clinical trials/research enrollment followed at six-months.

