**PROTOCOL TITLE: Education about Health and Cancer Study**

Providers will receive a BPA indicating patient may qualify to participate in the education survey. See enclosed invitation language. Providers will also have the option to include After Visit Summary (AVS) to Patient Notes that will contain invitation link. Patients will receive a link to the survey. If they choose to take part in the study, they will do so by completing the online consent, eligibility screening, pre-test, and contact information before the class they are registered for; attend the class; and complete the post-test after the class to assess achievement of the learning objectives. They will also be asked a series of questions to assess their eligibility for existing DCC clinical trials and research studies (see enclosed Qualtrics PDF).

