## **6.0 Procedures Involved\***

### **6.1 Experimental Arm 1 (Aim 1a):**

Out study will be largely advertised to DCC's patients and caregivers (e.g., through Patient and Family Support Services' catalog, DH events calendar, DCC/ DH Facebook, online listserves, waiting rooms)..

- a- Recruitment- recruitment to participate in the study will happen after a patient or caregiver receives a link to participate in survey from provider BPA. DCC providers open a message from electronic provider portal BPA. The BPA prompts an alert to providers – who open a message indicating the option to send a patient information about accessing the survey or, to be connected with a clinical nurse/coordinator who can walk the patient through the process of accessing the survey.  
1 – Provider portal option using electronic medical record portal EDH/Epic includes option inviting providers to click on Best Practice Alert when prompted.
- b- The recruitment language provides prospective participants with a link to an online survey where they can consent, complete eligibility screening, the pre-test, and contact information. Contact information (name, email, phone number, address) and date of birth is collected to facilitate: 1) hand-off to open studies/trials' teams and clinical staff (Research Nurses/Nurse Navigators) for recruitment, 2) tracking subsequent enrollment into any study/trial, 3) gift card distribution for their time, and 4) to invite them to

PROTOCOL TITLE: Education about Health and Cancer Study  
complete the post-test.

- d- Provision of participant compensation for completing pre-test. E-gift cards that have not been claimed six months after being emailed may be deactivated.
- e- Assignment of unique numeric identifiers to link records
- f- Completion of an online post-test survey (see attached Qualtrics PDF for Experimental Arm 1)- including:
  - Post-intervention knowledge
  - Pre-screening for eligibility into pre-selected open trials/studies at DCC(see attachment with study details and questions).
  - Post-intervention attitude and behavioral intention questions
- g- Provision of participant compensation for completing the post-test. E-gift cards that have not been claimed six months after being emailed may be deactivated.

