- h- Referral to pre-screened (possibly eligible) participants to PI's of pre-selected open studies/trials, as well as DCC clinical staff (research nurses, nurse navigators). This will entail providing participant contact/health information to PIs/study teams/DCC clinical staff of studies/trials that the participant may be eligible for. Participants will have provided permission for their information to be shared (see information sheet and pre-screening section of the Qualtrics post-survey). Tracking of participants' enrollment status into studies/trials over six months (via PI/study team records and DCC Office of Clinical Research records/Oncore).  
This will entail providing our participants' identifying information to the PIs/research teams of selected studies and to DCC's Office of Clinical Research and asking them to identify which participants have enrolled in studies/trials since the educational intervention. With permission/direction from DCC's Office of Clinical Research, our study team members may track enrollment via Oncore. See enclosed Excel spreadsheet that will be used for tracking. [We will also collect aggregate enrollment in trials/studies at DCC for comparison with our participants.]

**PROTOCOL TITLE:** Education about Health and Cancer Study

- i- Transmission of de-identified pre and post survey data files to NCI/CRCHD and/or its contractor for data entry, quality control, and national aggregation; e-mailing of tracking excel spreadsheet to NCI/CRCHD and/or its contractor.
- j- Local analysis of data to determine effect of study objectives

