**19.0 Provisions to Protect the Privacy Interests of Subjects**

19.1 and 19.2

Experimental Arm 1 (Aim 1a): Participants will complete the information sheet and study surveys online.

The information sheet provides information about how participants' contact/identifying information will be used. Those who pre-screen as being potentially eligible for an open study/trial will provide permission for their contact/identifying information to be shared with the study teams and/or the clinical team (e.g., Research Nurses/Nurse Navigators) (see enclosed pre-screening question sheet with permission question and information sheet).

Experimental Arm 2 and Control Arm (Aim 1b):

Contact/identifying information requested from participants will be managed and stored separately from the study data.

The information sheet provides information about how participants' contact/identifying information will be used. Those who pre-screen as being potentially eligible for an open study/trial will provide permission for their contact/identifying information to be shared with the study teams and/or the clinical teams (e.g., Research Nurses/ Nurse Navigators) (see enclosed information sheet and see Qualtrics PDF).

19.3 Any study forms containing identifiable information will not be available to all study members, with an exception of the Qualtrics account/survey, which will be managed by most study team members. Only the study coordinators and a manager/sub-investigator will have access to any other identifying information, and this information will only be accessed for purposes of gift card distribution and follow-up data tracking.

PROTOCOL TITLE: Education about Health and Cancer Study

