## **24.0 Setting**

**24.1** Study planning and procedures will mostly take place in office space in the Rubin 8 building at DHMC (although in-person events will take place throughout New Hampshire and Vermont).

Experimental Arm 1 (Aim 1a):

Recruitment for Experimental Arm 1 will take place through email invitation, and the surveys will be accessed online through Qualtrics. Participants will attend the class by Zoom or in-person at an DCC site.

Experimental Arm 2 (Aim 1b):

Recruitment for Experimental Arm 2 and Control Arm will primarily take place through social media (e.g., Facebook), listserves, flyers, and other online opportunities (as described earlier), and the surveys/intervention will be accessed online through Qualtrics.

DCC does have a Community Advisory Board that is administered by study member [name] and/or [name]. Board members include cancer survivors and caregivers, community members, public health researchers, healthcare organizations, and non-profit representatives. We may consult with the Community Advisory Board regarding:

- Content of video and/or review of video and website materials
- Review of aggregate, de-identified results
- Next steps after this study is complete; steps regarding sustainability of video and/or in-person outreach

We will also work with our Patient Family Advisory Committee (composed of cancer survivors, family members to cancer survivors, and community-based allies) to receive and incorporate input on the educational video and website materials. We will also work with our internal Clinical Trials Advisory Board members (composed of Clinical Trials staff, Radiation Oncologists, Senior Leadership and our DCC Marketing & Communications Team, etc.) for the same purpose.

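### Section 14.2 makes six-month enrollment follow-up in Arm 1 depend on an in-person pre-test, but the protocol puts every Arm 1 survey online

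*Protocol*

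**What the plan says.** **The rule.** For Experimental Arm 1, Section 14.2 states: "Individuals who do not complete the in-person pre-test, education, post-survey, and contact/identifying information will not have their clinical trials/research enrollment followed at six-months". The Arm 2 sentence in the same section lists the same four items without the word *in-person*. Section 14.1, the general withdrawal rule, requires pre-test, education and post-test and names no mode.

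**How Arm 1 is surveyed.**
- Section 5.1 has participants "completing the online consent, eligibility screening, pre-test, and contact information before the class they are registered for".
- Section 6.1, step b, gives them "a link to an online survey where they can consent, complete eligibility screening, the pre-test, and contact information". Step f makes the post-test an online survey as well.
- Sections 19.1 and 19.2 say of Arm 1: "Participants will complete the information sheet and study surveys online".
- Section 24.1 has the Arm 1 surveys accessed online in Qualtrics. The class alone has a choice of mode: "Participants will attend the class by Zoom or in-person at an DCC site".

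**What is meant to be tracked.** Section 6.1, step h, provides for "Tracking of participants' enrollment status into studies/trials over six months (via PI/study team records and DCC Office of Clinical Research records/Oncore"), with no condition on how the surveys or education were completed. Section 4.2 names enrollment over six months as an endpoint. It is also part c of hypothesis 1 (Section 2.2) and part of Aim 1a (Section 2.1).

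**The concern.** The sentence in Section 14.2 is an operative rule. It determines whose later enrollment in a trial or study is looked up, and so who can contribute to the Section 4.2 endpoint in Arm 1. It sets a condition that the described Arm 1 procedures give nobody a way to meet.

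Two parts of the current protocol therefore give staff opposite instructions. Under Section 14.2, an Arm 1 participant who did everything asked, but online, is not followed. Under step h, the same person is tracked, and identifying details go to study teams and the Office of Clinical Research for that purpose. If Section 14.2 prevailed, the enrollment part of Aim 1a and hypothesis 1c would have no Arm 1 data, and the enrollment comparison in Aim 1c would lack one of its two arms.

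The rule governs whether data are collected at all, so this is not a detail that can be left to an analysis plan. The point concerns only the mode condition. It takes no position on whether people who do not complete the study should also be followed.

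**Working it through.** The check is mainly a comparison of text, because the point rests on no power, alpha or effect-size figure.

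**Step 1. The condition and its consequence.** Section 14.2, Arm 1: "Individuals who do not complete the in-person pre-test, education, post-survey, and contact/identifying information" is the condition, and "will not have their clinical trials/research enrollment followed at six-months" is the consequence. The adjective stands directly before the pre-test.

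**Step 2. Can the condition be met?**

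| Arm 1 item | Mode described | Where |
|---|---|---|
| Pre-test | Online | 5.1; 6.1 step b; 19.1 and 19.2; 24.1 |
| Post-test | Online | 6.1 step f; 19.1 and 19.2; 24.1 |
| Contact information | Online, with the pre-test | 5.1; 6.1 step b |
| Class | Zoom or in person | 24.1 |

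The pre-test has no in-person route in any section. Section 25.0 says that staff can be engaged to administer pre-tests and post-tests, but gives neither a mode nor an arm.

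**Step 3. Apply the rule to the ways an Arm 1 participant can complete.**
- Online surveys with an in-person class: no in-person pre-test, so not followed.
- Online surveys with a Zoom class: no in-person pre-test, so not followed.
- Online surveys reached through the provider alert, with portal or video education: no in-person pre-test, so not followed.

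**Step 4. Compare with the parallel rules.** Section 14.1, the Arm 2 sentence in Section 14.2 and Section 6.1 step h contain no mode condition. Each of the three records above would be followed if the Arm 1 sentence were worded like the Arm 2 sentence.

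**Step 5. Size.** Section 12.0 gives targets of up to 50 completers in Arm 1 and 200-250 in Arm 2. It also expects up to 900 consents with about one third completing: 900 x 1/3 = 300 = 50 + 250, which agrees with the upper ends of the targets.
- Literal rule: 0 of up to 50 Arm 1 completers are followed.
- With the word deleted: all Arm 1 completers, up to 50, are followed.
- As a share of all planned completers, with 50 in Arm 1: 50/(50 + 250) = 16.7% to 50/(50 + 200) = 20%.

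The protocol gives no power or precision target for Arm 1 enrollment, so there is no planned figure to reproduce.

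**The case against.** **A stale word that nobody will apply.** This is the strongest objection, and much of it stands. The literal condition would visibly empty the arm, and staff have clear text pointing the other way in Section 4.2, Section 14.1 and step h. The revision history explains how the word could have survived: revision 4 still describes Arm 1 as in-person, and revision 9 supplies electronic pre- and post-surveys for it. That history shows only the likely origin. The contradiction itself lies between sections of the current text. The objection lowers the chance of harm but does not make the rule correct. *In-person* is also still live vocabulary elsewhere, for class attendance and events in Section 24.1 and for in-person outreach in Section 17.3, so a reader cannot be sure that it is dead text here.

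**An online survey could be filled in on site.** Section 6.1 lets a nurse or coordinator help a patient reach the survey. The protocol does not call that an in-person pre-test and does not make it a condition of tracking.

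**A stronger reading that a reader might infer.** One could take *in-person* to govern the class, so that Zoom attendees are dropped and those who remain are a selected, more engaged group. The documents do not support this. The word precedes the pre-test, and the reading requires staff to ignore it for both surveys yet enforce it for the education. The Zoom share is not given, so the number lost cannot be stated. Nothing shows that people who attend at a site enroll more often, and Section 1.0 already describes a target population connected with the cancer center. No claim of bias is made here.

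**Conclusion.** The Arm 1 follow-up rule in Section 14.2 is wrong as written. Taken literally, it follows none of the up to 50 Arm 1 completers for the enrollment endpoint, contrary to step h of Section 6.1. This rests on one assumption: that a survey completed online in Qualtrics is not an in-person pre-test.

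A reader might infer that the Arm 1 enrollment data will in fact be lost. The documents do not support that. The word is probably a remnant, and the team may well follow step h. The total loss is what the rule says, and it is not a forecast. Knowledge, attitude and intention outcomes from the surveys are not touched by this sentence.

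The correction is worth making because the sentence decides who is followed for a named endpoint and the change is trivial.

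**What to change.** In Section 14.2, Experimental Arm 1, delete *in-person*, so that the sentence reads like its Arm 2 counterpart and agrees with Section 14.1. At the same time, check the sentence against Section 6.1 (steps b, f and h), Sections 19.1 and 19.2, and Section 24.1, so that all of them describe the same group for six-month tracking.

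Nothing more follows from this contradiction. There is no need to record mode of attendance. Deleting the word also does not settle whether the Arm 1 education is the class or the portal material, which is a separate question.

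The cost is one word in the next protocol modification. It needs no new data, staff or participants, because step h already plans the record look-up for this arm.

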#### Experimental Arm 2 (Aim 1b):

Any participant can discontinue participation at any time by closing the window on their device’s screen that contains our survey content. Individuals who do not complete the pre-test, education, post-survey, and contact/identifying information will not have their clinical trials/research enrollment followed at six-months.

PROTOCOL TITLE: Education about Health and Cancer Study

**15.0 Risks to Subjects\***

**15.1** Because this activity is primarily educational, the risks are minimal. However, some participants with a family history of cancer or who have had negative experiences with clinical trials and research may be distraught by participating. Additionally, as with the collection of any identifiable information, there is minimal risk that confidentiality could be breached. However, we will have several safeguards in place, as described in Section 17 and in the attached document entitled *Data Collection Storage and Security*.

Because the risks are unlikely and minimal, we feel that they're reasonable in relation to the knowledge that participants will gain, as well as the knowledge that NCI/CRCHD and DCC will gain.

15.2-15.4. N/A

